### 3. SUMMARY OF MODIFICATIONS

#### 3.1 Modifications from the Approved Clinical Study Protocol

There are no modifications from the approved Clinical Study Protocol (CSP) (Version 4.0, 12 April 2017).

#### 3.2 Modifications from the Approved Statistical Analysis Plan

This is the first version of the Statistical Analysis Plan (SAP) for the final analysis of the study.

### 4. INTRODUCTION

This final Analysis Plan is based on the information contained in the CSP VX15-770-123 Version 4.0, dated 12 April 2017.

Vertex Biometrics department or a designated contract research organization (CRO) will perform the statistical analysis of the efficacy and safety data; SAS version 9.4 or higher will be used to generate all statistical outputs (tables, figures, listings, and datasets). The SAP will be finalized and approved prior to the clinical database lock.

Following review of study enrollment and assessment of the available number of potential subjects for this study, Vertex decided to close enrollment as of 21 February 2017 and withdraw subjects in order to terminate the study. After the protocol amendment has been approved at a site, subjects in Part 1 will be withdrawn from the study at their Week 24 Visit, and subjects in Part 2 will be withdrawn from the study and requested to complete the Early Termination of Treatment Visit. The SAP text will use original text from the protocol for objectives and study design, however, the final analysis will be based mainly on Part 1 data due to the small amount of data available for Part 2.

### 5. STUDY OBJECTIVES

#### 5.1 Primary Objective

To evaluate the efficacy of ivacaftor treatment, as measured by LCI, in subjects with CF who have a specified *CFTR* gating mutation and are 3 through 5 years of age at the start of the study

#### 5.2 Secondary Objectives

To evaluate the following in subjects with CF who have a specified *CFTR* gating mutation and are 3 through 5 years of age at the start of the study:

- Disease progression as measured by changes in pancreatic function
- The safety of ivacaftor treatment

## 6. STUDY ENDPOINTS

### 6.1 Part 1

#### 6.1.1 Primary Endpoint

- Absolute change from baseline in LCI2.5 through 8 weeks of treatment

#### 6.1.2 Secondary Endpoints

- Absolute change from baseline in serum levels of immunoreactive trypsinogen at 8 weeks of treatment
- Absolute change from baseline in fecal elastase-1 at 8 weeks of treatment
- Absolute change from baseline in weight at 8 weeks of treatment
- Absolute change from baseline in body mass index (BMI) at 8 weeks of treatment
- Safety, as determined by AEs, clinical laboratory values (including liver function tests (LFTs) ), ophthalmologic examinations (OEs), physical examinations, and vital signs

## 7. STUDY DESIGN

### 7.1 Overview of Study Design

This is a 2- part, randomized, double- blind, placebo- controlled, crossover study with a long-term open- label period. A schematic figure of the study design is presented in Appendix A.

In addition to the Screening Period (up to 4 weeks in duration), subject participation is anticipated to last approximately 148 weeks (2 Treatment Periods of 8 weeks each, Washout Period of 8 weeks, Open -label Period of 120 weeks, and Follow-up Telephone Contact approximately 4 weeks after last dose of study drug).

Subjects will be randomized 1:1 to receive 1 of 2 treatment sequences during Part 1:

- Sequence 1: ivacaftor in Treatment Period 1 → washout → placebo in Treatment Period 2
- Sequence 2: placebo in Treatment Period 1 → washout → ivacaftor in Treatment Period 2

This study includes:

- Screening Period: Day -28 through Day -1 relative to the first dose of study drug
- Part 1 Treatment Period 1 through Treatment Period 2

- Treatment Period 1: Day 1 (first dose of study drug) through Week 8
- 8-week Washout Period
- Treatment Period 2: Week 16 through Week 24
- Part 2 Open-label Period: Week 24 through Week 144 (the first dose of ivacaftor during the Open-label Period will be given after completion of assessments at the Week 24 Visit); the Week 24 Visit (Part 1) is also considered the first visit of the Open-label Period.
- Follow-up Telephone Contact (4 weeks [ $\pm 7$  days] after the last dose of study drug)

Subjects who prematurely discontinue study drug treatment will be required to complete the Early Termination of Treatment Visit, which is to be scheduled as soon as possible after it is decided that the subject will terminate study drug treatment. Subjects who prematurely discontinue study drug treatment will also be required to complete the Safety Follow-up Visit, approximately 4 weeks ( $\pm 7$  days) after their last dose of study drug. If the Early Termination of Treatment Visit occurs 3 weeks or later following the last dose of study drug, then the Early Termination of Treatment Visit will replace the Safety Follow-up Visit, and a separate Safety Follow-up Visit will not be required.

Subjects will continue to complete all other scheduled study visits for assessments of efficacy and other endpoints as detailed in the Schedule of Assessments. Subjects who discontinue study drug treatment during Part 1 will not be allowed to participate in Part 2 of the study.

## 7.2 Sample Size and Power

It is planned that up to a maximum of approximately 50 subjects will be enrolled in this study. As shown in Table 7.1, a sample size of 50 subjects will provide approximately 80% power to detect a treatment difference in mean change from study baseline in LCI (difference between ivacaftor and placebo in the change from study baseline) of 1.5 points. The calculation is based on a paired t-test with a 2-sided significance level of 0.05, and assumes that the within-subject standard deviation (SD) for the difference in change from study baseline for the 2 periods is 3.5 points, and that the dropout rate is about 10% for Part 1.

Different scenarios are presented in Table 7.1 for the variability and the magnitude of the treatment effect based on 80% power and 2-sided significance level of 0.05. The most conservative scenarios are presented in the last 2 rows of the table (i.e., treatment effect of 1.0 and 1.5, respectively).

**Table 7-1 Sample Size Calculation Corresponding to Different Values of Treatment Effect on Lung Clearance Index Change-From-Predose**

Treatment Effect (points) on LCI Change From Study Baseline	Standard Deviation of Paired Treatment Difference in LCI Change From Study Baseline	N
1.0	1.0	12
1.0	1.2	15
1.0	1.5	22
1.0	1.8	31
1.0	2.0	37
1.0	2.2	45

**Table 7-1 Sample Size Calculation Corresponding to Different Values of Treatment Effect on Lung Clearance Index Change-From-Pre-dose**

Treatment Effect (points) on LCI Change From Study Baseline	Standard Deviation of Paired Treatment Difference in LCI Change From Study Baseline	N
1.5	3.5	50

### 7.3 Randomization

In Part 1, subjects will be randomized in a 1:1 ratio to:

Treatment Sequence 1 (ivacaftor → washout → placebo) or  
 Treatment Sequence 2 (placebo → washout → ivacaftor).

Part 2 is open-label. Randomization is not required for Part 2 because all subjects will receive ivacaftor.

#### 7.3.1 Blinding

Part 1 is a double-blind study. The subjects and all site personnel, including the investigator and the study monitor, will remain blinded to treatment assignments until database lock. The Vertex study team will remain blinded to treatment assignments until all subjects have completed Part 1 of the study.

All study personnel will be blinded to subject treatment assignments except for the following individuals:

- Any site personnel for whom this information is important to ensure the safety of the subject in the event of a life-threatening medical emergency
- Vertex Global Patient Safety (GPS) and Regulatory Affairs personnel to satisfy SAE processing and reporting regulations
- Unblinded statistician preparing the final (production) randomization list who is not part of the study team
- Vendor preparing the unblinded analysis for the IDMC
- Vertex Data Management IWRS management
- Vertex Clinical Supply Chain

#### LCI Data Blinding

Despite treatment blinding, knowledge of the LCI results has the potential to suggest whether a subject has been administered active study drug or placebo. Therefore, during Part 1, the Vertex study team will have no access to the post-dose LCI data.

## 8. ANALYSIS SETS

### 8.1 Full Analysis Set

The **Full Analysis Set** (FAS) is defined as all randomized subjects who have a *G551D*, *G178R*, *S549N*, *S549R*, *G551S*, *G1244E*, *S1251N*, *S1255P*, or *G1349D* mutation on at least 1 allele and who received at least 1 dose of study drug (i.e., ivacaftor or placebo) and had at least one post-baseline assessment. In the FAS, subjects will be analyzed according to the treatment sequence they were randomized to.

### 8.2 Safety Set

The **Safety Set** is defined as all subjects who received at least 1 dose of study drug. All summaries of safety will be referenced using the Safety Set, and will be performed per treatment received.

## 9. STATISTICAL ANALYSIS

### 9.1 General Considerations

The study assessments and time points schedule is provided in [Appendix B](#).

**Continuous variables** will be summarized using the following descriptive summary statistics: the number of subjects (n), mean, standard deviation (SD), standard error (SE), median, minimum value (min), and maximum value (max).

**Categorical variables** will be summarized using counts and percentages.

**Baseline Value:** For this crossover study, 2 types of baseline (study baseline and period baseline) will be defined for Part 1.

For Part 1: The study baseline is defined as the most recent non-missing measurement collected prior to the initial administration of study drug in Treatment Period 1. Period baseline is defined as the most recent non-missing measurement collected before the initial administration of study drug in each Treatment Period. For Treatment Period 1, the period baseline will be the study baseline; for Treatment Period 2, the period baseline will be from an assessment measured after the Washout Period.

For Part 2: The study baseline is defined as the most recent non-missing measurement collected prior to the initial administration of study drug of Treatment Period 1. Period baseline is defined as follows:

For Treatment Sequence 1 (ivacaftor->washout->placebo), period baseline will be defined as the most recent non-missing measurement collected prior to initial administration of ivacaftor in the Open-label Period (Part 2).

For Treatment Sequence 2 (placebo->washout->ivacaftor), period baseline will be the same as period baseline for Treatment Period 2 in Part 1 (i.e., the Week 16 Visit).

Efficacy analyses will be based on change from study baseline. However, efficacy analyses based on change from period baseline will also be presented. Similarly, summary tables, as applicable, will be presented based on both baselines.

**Treatment Emergent (TE) Period:**

- For Treatment Period 1 of Part 1, the TE period will be from the first dose of study drug in Treatment Period 1 of Part 1 to the earliest of the following:
  - 1) 28 days after the date of subject's treatment completion during Treatment Period 1
  - 2) Safety Follow-up Visit if discontinued study early during Treatment Period 1
  - 3) 28 days after the last dose of the study drug for subjects who discontinued the study early during Treatment Period 1 and do not have a Safety Follow-up Visit
- For Treatment Period 2 of Part 1, the TE period will be from the first dose of study drug in the Treatment Period 2 of Part 1 to the earliest of the following:
  - 1) The date of treatment completion of Treatment Period 2
  - 2) Safety Follow-up Visit if discontinued study early during Treatment Period 2
  - 3) 28 days after the last dose of the study drug for subjects who discontinued the study early during Treatment Period 1 and do not have a Safety Follow-up Visit
- For Part 2, the TE period will be from the first dose of study drug in Part 2 to the earliest of the following:
  - 1) The Safety Follow-up Visit,
  - 2) 28 days after the last dose of the study drug for subjects who discontinued the study during Part 2 and do not have a Safety Follow-up Visit,

**Visit Windowing Rules:** Appendix C defines the windows for protocol-defined visits. The windows will be applied using the following rules for both scheduled and unscheduled visits. If no measurement is available within a visit window, the assessment will be considered missing for the visit. If there is more than one measurement available within the same visit window, the following rules will be used:

- For all safety parameters, if there are multiple measurements within a visit window, then 1) the record closest to the target day will be used, with the exception of the threshold analysis in which the worst record will be used; 2) if there are multiple records within the same distance of the target day, the latest record will be used; or 3) the Safety Follow-Up (SFU) visit will not be windowed; instead, the nominal visit will be used in relevant analyses.
- For all efficacy parameters, if there are multiple measurements within a visit window, the record at the scheduled visit will be used. Otherwise,
  - If there are no measurements at the scheduled visit, then the record closest to the target day will be used;
  - If there are multiple records with the same distance to the target day, the latest record will be used.
  - Assessments at the early treatment termination (ETT) visit will follow the windowing rules for regular visits.
  - Assessments at safety follow-up (SFU) visit will follow the windowing rules for regular visits if they fall within the upper boundary of the window for the last scheduled visit; it will remain as the SFU if it goes beyond the upper boundary of the window for the last scheduled visit.

**Incomplete/Missing data:** Missing data (e.g., dates) will remain as missing in the listings, and conservative conventions established will be used to derive specified parameters for summaries.

**Outliers:** No formal statistical analyses will be performed to detect and/or remedy the presence of statistical outliers.

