### 9.4.1 Adverse Events

For analysis purposes, adverse events will be classified as pre-treatment emergent, TEAE, or post-treatment emergent. Adverse events which start (or increase in severity) during the period from the signing of informed consent up to, but not including, the first dose of study drug will be considered pre-treatment. Adverse events which start (or increase in severity) during the period from the first dose of study drug through completion of the Follow-up Visit will be considered TEAE. Adverse events which start (or increase in severity) after the completion of the Follow-up Visit will be considered post-treatment adverse events.

If an adverse event started (or increased in severity) during a specific treatment period, this adverse event will be attributed to the study drug the subject is receiving during this Treatment Period. Adverse events that started (or increased in severity) during the Washout Period and within 28 days of the last dose of treatment period 1 will be attributed to the treatment received in Treatment Period 1. Please see Section 9.1 for details.

For determining whether the AEs with missing or partially missing dates are treatment-emergent, please refer to Appendix D for rules. Please note that no imputation will be displayed in the listing outputs.

Adverse event summary tables will be presented for TEAE only and will include the following:

All TEAEs,

Related (defined as possibly related or related) TEAEs,

TEAEs leading to treatment discontinuation,

Serious TEAEs,

TEAEs by severity,

TEAEs by relationship.

Summaries will be presented by MedDRA system organ class and preferred term using frequency counts and percentages (i.e., number and percentage of subjects with an event). Subjects with multiple occurrences of the same adverse event or a continuing adverse event will be counted once, and only the maximum severity level will be presented in the severity summaries, and the worst/highest relationship level in the relationship summaries. In addition,

listing containing individual subject adverse event data for all deaths and other serious and significant adverse events will be provided, separately. All adverse events including Pre- and Post-treatment adverse events will be presented in individual subject data listings.

Imputation rules for missing or partial AE dates are presented in Appendix D.

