### If only Day of AE start date is missing:

If the AE start year and month are the same as that for the first dose date, then:

- If the full (or partial) AE end date is NOT before the first dose date or AE end date is missing, then impute the AE start day as the day of first dose date; otherwise, impute the AE start day as 1.
- Otherwise, impute the AE start day as 1.

Compare the imputed AE start date with TE period to determine whether the AE is pretreatment AE, TEAE or post-treatment AE.

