### If Day and Month of AE start date are missing:

If AE start year = first dose year, then:

- If the full (or partial) AE end date is NOT before the first dose date or AE end date is missing, then impute the AE start Month and Day as the Month and Day of first dose date; otherwise, impute the AE start Month as January and the Day as 1.
- Otherwise, impute the AE start MONTH as January and the DAY as 1.

Compare the imputed AE start date with TE period to determine whether the AE is pretreatment AE, TEAE or post-treatment AE.

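### SAP Appendix D dates partly dated AEs from one first dose date in a two-period crossover, so a partly dated Period 2 AE can leave the TEAE tables or move to the other treatment (minor)

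*SAP*

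**What the plan says.** **Partial dates.** SAP 9.1 promises that, where data such as dates are missing, "conservative conventions established will be used to derive specified parameters for summaries". Appendix D supplies the rules for AE start dates:

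- Only the day missing: the test is "If the AE start year and month are the same as that for the first dose date, then". If it is met and the AE did not end before that dose, the start is set to the first dose day. In any other month it is set to day 1.
- Day and month missing: if the year is that of the first dose and the AE did not end before it, the rule is to "impute the AE start Month and Day as the Month and Day of first dose date". In any other year the date becomes 1 January.
- Year missing: the site is queried and nothing is imputed. The AE counts as a TEAE unless it ended before the first dose.

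After imputation the instruction is to "Compare the imputed AE start date with TE period to determine whether the AE is pretreatment AE, TEAE or post-treatment AE". Appendix D never says which period's first dose it means.

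**Windows.** SAP 9.1 runs the Period 1 window to 28 days after treatment completion. The Period 2 window ends at the earliest of three points. The first is "The date of treatment completion of Treatment Period 2". The third, printed under Period 2, is "28 days after the last dose of the study drug for subjects who discontinued the study early during Treatment Period 1" where there is no Safety Follow-up Visit.

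**AE section.** SAP 9.4.1 says that AEs arising "from the first dose of study drug through completion of the Follow-up Visit will be considered TEAE". It attributes washout AEs "within 28 days of the last dose of treatment period 1 will be attributed to the treatment received in Treatment Period 1", and then refers to 9.1 for details. AE tables cover TEAEs only; listings cover every AE.

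**Collection.** Protocol 13.1.1.3 collects AEs from subjects without a Safety Follow-up Visit until 28 days after the last dose, or until an Early Termination Visit held 3 weeks or more after it, whichever is earlier. The schedule of assessments has collection run to the end of study participation. After the amendment, Part 1 subjects leave at Week 24 and need no Safety Follow-up Visit (Protocol 8.1).

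**The concern.** In this crossover the period determines the treatment. A start date moved across a period boundary therefore changes whether an AE is tabulated and under which treatment. A single anchor suits a parallel-group trial, where it pulls doubtful AEs into the treated time. Here it does that for Period 1 only. For Period 2 the same rule can push an on-treatment AE back into the washout or onto the other treatment, which is the opposite of a conservative convention. When the year is missing, the AE is a TEAE but no period follows from the rule.

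The protocol names TEAE incidence as the key safety endpoint (12.3.5), and the SAP calls the sample size low (9.3.1). One reclassified subject can therefore be visible in a percentage.

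**Working it through.** The plan states no figure on this point, so the check applies the rules to the calendar.

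**Inputs**
- Period 2 starts 16 weeks = 112 days after Day 1, so on study day 113 (Protocol 8.1).
- Period 1 completion on study day 56 or 57 gives a window end on day 84 or 85 (+28, SAP 9.1).
- Enrollment closed on 21 February 2017 (Protocol 8.1). Adding 112 days gives a last nominal first Period 2 dose on 13 June 2017.
- Assumed: 56 dosing days in Period 2; onset equally likely on each; an AE end date that is missing or not before the first dose; first dose date read as the first dose in the study; four trial ranges for the first Period 2 dose, all ending 13 June 2017. The documents do not give the actual dates.

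**Time in neither window.** 113 − 1 − 84 = 28 days, or 27 with day 85. With the ±5-day washout allowance the range is 22 to 33 days.

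**Only the day missing.** An AE is moved to before the Period 2 dose only if it starts in the calendar month of that dose and the dose was not on the 1st. For a dose on day j (j > 1) of a month with M days, M − j + 1 dosing days are moved. Summed over all j, a month gives M(M − 1)/2: 465 for 31 days, 435 for 30, 378 for 28.

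For first Period 2 doses from 1 January to 13 June 2017:
- Moved: 465 + 378 + 465 + 435 + 465 + (29 + 28 + … + 18 = 282) = 2,490.
- Total: 164 start dates × 56 = 9,184.
- Share: 2,490 / 9,184 = 27.1%.

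| First Period 2 doses from | Moved / total | Day missing: moved before Period 2 dose | Day and month missing: placed in Period 1 window |
|---|---|---|---|
| 1 Jan 2017 | 2,490 / 9,184 | 27.1% | 82.3–82.9% |
| 1 Oct 2016 | 3,855 / 14,336 | 26.9% | 77.9–78.3% |
| 14 Jun 2016 | 5,373 / 20,440 | 26.3% | 84.5–84.8% |
| 14 Dec 2016 | 2,661 / 10,192 | 26.1% | 75.9–76.4% |

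Of the day-missing shares, only 0.1 to 0.3 percentage points land in the Period 1 window; the rest land in neither window. The ranges in the last column are for completion on day 56 or 57. That column includes dates set to 1 January where this falls in the Period 1 window.

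**Example.** First dose 28 January 2017; Period 1 window ends 21 or 22 April; Period 2 starts 20 May (28 January + 112 days). An AE begins on 25 May. Recorded as May 2017, it becomes 1 May and falls in no window. Recorded as 2017, it becomes 28 January and counts under the Period 1 treatment.

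**Effect of one subject.** An incidence changes by 100/n points: 20 at n = 5, 10 at n = 10, 4 at n = 25. These n are assumed.

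**Item 3 of the Period 2 rule.** Read literally, it gives no 28-day limit to a Period 2 discontinuer without a Safety Follow-up Visit. But Protocol 13.1.1.3 stops collection for such a subject by 28 days after the last dose, so an open window and the intended one hold nearly the same AEs.

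**Period 2 end.** For a subject withdrawn at Week 24, SAP 9.1 allows 0 days after completion, against 28 days in Period 1 and up to 28 days of collection under Protocol 13.1.1.3. The schedule's end of study participation points to Week 24 instead. These are calendar days, not events.

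**The case against.** The strongest reply is that first dose date can be read as the first dose of the relevant period, which removes most of the problem. Appendix D also states its purpose as deciding whether an AE is treatment-emergent; attribution to a treatment belongs to 9.4.1. Missing data are queried (Protocol 13.3), so few partial dates should survive, and dates lacking both day and month should be rarer still. Safety is descriptive and every AE is listed. All of this limits the effect. It does not settle the rule: Appendix D does not say per period, whereas 9.1 names the period when it means one, and the SAP gives no other date by which to assign a partly dated AE to a treatment.

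Four stronger readings are tempting, and the documents do not support them.

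- *That a quarter or more of Period 2 AEs will be misclassified.* The percentages are shares of calendar days, conditional on a partial date and on the literal reading. The documents give no count of AEs, partial dates or subjects.
- *That 9.1 and 9.4.1 are in open conflict over late-washout AEs.* The wording of 9.4.1 is loose, but it points to 9.1, and Appendix D sorts by the 9.1 windows. Leaving an AE more than 28 days off drug without a treatment also fits Protocol 12.3.5.1, which attributes AEs by the treatment being received at onset.
- *That the Period 2 window wrongly discards follow-up.* Ending at completion is coherent for subjects who go straight into Part 2. For those withdrawn at Week 24 no contact is scheduled afterwards, so a 28-day tail would be poorly ascertained and is debatable. What stands is that the passages disagree.
- *That SAP 3.1 conceals a departure from the protocol.* The protocol leaves detail to the SAP, and adding end dates where it is silent is elaboration. Noting it would be documentation only.

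**Conclusion.** The point holds as a minor defect. Followed as written, Appendix D mishandles partly dated Period 2 AEs: about 26% to 27% of Period 2 dosing days are exposed when the day is missing, nearly always by loss from both windows, and 76% to 85% when day and month are missing, by transfer to the other treatment. An AE with no year has no period. This is not the conservative handling that 9.1 promises. The figures rest on nominal visit timing, uniform onset, assumed start-date ranges and a single study-level anchor. The number of AEs affected is unknown and could be zero.

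The item 3 error is certain from the text but has little practical effect. The Period 2 end rule is a real inconsistency between SAP 9.1, Protocol 13.1.1.3 and the schedule, and the documents do not settle it. No test or error rate is touched.

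**What to change.** Before database lock:

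1. Apply Appendix D to the first dose date of each treatment period. When the partial date matches the month of the first Period 2 dose and the AE did not end before that dose, impute to that dose. This removes the day-missing loss computed above; the price is that some washout AEs from the same month will count under Period 2. For an AE whose date still fits both periods after the query, including one with no year, state in advance the treatment to which it is assigned, and footnote it.
2. In item 3 of the Period 2 rule in SAP 9.1, replace Treatment Period 1 with Treatment Period 2.
3. Have SAP 9.4.1 cite the 9.1 windows as the only TEAE definition.
4. Reconcile the Period 2 end rule for subjects not entering Part 2 with Protocol 13.1.1.3 and the schedule. One way is to show AEs up to 28 days after the last dose in the table, or as a footnoted sensitivity count. State that no scheduled contact covers that time for subjects withdrawn at Week 24.

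The cost is SAP wording and programming. No new data are needed.
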